Protocol for TMS-Neurofeedback Stroke Experiment

NCT Number (not yet assigned)

Date: 18/10/23

1. Overview

Upper limb weakness following a stroke affects most survivors and is a key factor in preventing them from returning to independent activities of daily living. Most of the current state-of-the art approaches to rehabilitation require that the patient can generate some activity in the paretic limb, which is not possible for many patients in the early period following stroke, nor for some patients even in the chronic period. This delays and prevents their participation in physical therapies. Approaches that enable more patients to engage with movement therapies at an earlier timepoint during the 'sensitive period' following stroke are greatly needed.

Despite having no functional movement in the paretic limb, most stroke patients exhibit Motor Evoked Potentials (MEPs) when stimulated over the damaged motor areas of the brain using Transcranial Magnetic Stimulation (TMS). This indicates intact pathways from the brain to the muscles and has been shown to predict better subsequent functional recovery (*Stinear et al, 2012; Byblow et al. 2015*). In the early days following stroke, the excitability of neuronal pathways from the brain to the muscles is substantially reduced. This most likely reflects the demyelination of axons, leading to conduction failure. Within the first 12 weeks, a degree of spontaneous proportional recovery of motor function typically occurs, up to 70% of the individual's maximum possible improvement. Interestingly, this time course of recovery coincides with the resolution of corticomotor excitability (MEP amplitudes), which also resolves to 70% of normal levels within the same 12 week period (*Byblow et al. 2015; Cincinelli et al., 2003; Thickbroom, Byrnes, Archer, & Mastaglia, 2004*). The interconnectedness of the functional recovery process and resolution of corticomotor excitability provides some insight into the neurobiology of spontaneous motor recovery and raises the intriguing possibility that perhaps interventions directly targeting the neural mechanisms of corticomotor excitability in this sensitive period would causally impact upon and accelerate recovery.

In the absence of being able to generate movement in the paretic limb, motor imagery has been suggested to activate many of the same brain-muscle circuits as actual movement. However, as imagery is a hidden mental process, it is impossible for individuals to gauge what impact this is having upon their neural activity, to learn how to best exploit this mechanism to augment stroke recovery.

This research project is an investigation into the mechanisms and efficacy of using a novel brain-computer interface (BCI) (eg. Ruddy et al., 2018) based upon muscle responses to TMS to provide feedback (visual and auditory) to stroke survivors while they perform motor imagery.

Using this approach, magnetic pulses will be applied to the scalp over the location on the motor cortex that controls the arm and hand, via TMS. This evokes a twitch in the stroke-affected muscles (the MEP), which is recorded using electromyography (EMG). The size of MEPs are displayed to the patient in real-time, with rewarding visual and auditory feedback incorporated in a game-like display. The patient is instructed to learn how to make MEPs bigger using motor imagery, guided by the feedback from the brain-computer interface.

We hypothesise that training using TMS-neurofeedback will lead to increases in MEP amplitudes, compared to a control group receiving pseudofeedback. We will investigate whether these changes in MEP amplitudes correlate with enhanced or faster than usual functional improvement and explore the underlying structural and neurochemical brain mechanisms of recovery.

2. Patient characteristics and exclusion criteria

20 patients (10 in TMS NF group, 10 in Pseudo-feedback group). Sub-acute: 2-26 weeks post stroke. Would prefer 2-12 weeks if feasible as there is a critical period in first 12 wks. First stroke (no previous TIAs). Single Hemisphere lesion. Low/No residual movement in lower arm and hand. MEP positive (in response to TMS). No or negligible OCS broken hearts cancellation test score (visual neglect) 6. No or almost no cognitive impairment (Pass or near pass MMSE and MOCA) 7. Passes TMS-Safety Questionnaire (no contraindications to TMS)

3. Recruitment Procedure

Patients informed about the study directly via consultant [name] and his team and provided with information sheets detailing how to contact the researchers if interested.

4. Procedures with Patients

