4.1 Informed Consent and Providing Information

The patient should be asked to read through the information sheet prior to coming to the first day of the experiment. However, when they arrive for the first session, provide them again with the information sheets and go through them page by page reading and explaining everything to them, answering any questions. When the patient has understood everything, read through the consent form with them, answering any questions, and if they consent to participate ask them to sign their name. If they are unable to sign the consent form, their next of kin can provide consent by proxy. At this stage they will be assigned an

anonymous code which will be used to identify their data and assigned to Group A or Group B using a computer algorithm.

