At this stage, if the patient has no MEPs in response to TMS, unfortunately they will not be able to participate further in the study (or, if willing, try again in a week to see have MEPs recovered).

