4.5.2 TMS neurofeedback block

The patient will be positioned in front of a computer monitor and will receive a block of 20 neurofeedback trials. Each trial contains just one TMS pulse, so in total they will receive 20 TMS pulses (at an intensity that is 120% of the RMT) with an interval of 6-8 seconds between pulses. Each TMS pulse will be followed immediately by feedback on screen in the form of a vertical bar. The height of the bar indicates the amplitude of the MEP recorded in the muscle, and this is shown relative to a horizontal white line that indicates their baseline MEP amplitude. If the current MEP on a given trial is larger than baseline, the trial is deemed 'successful'. The vertical bar will be green, with a green tick on screen beside it, and a positive sound-byte will be played. If the MEP amplitude is below baseline, the trial is unsuccessful; The bar will be red, with a red cross, and a negative sound-byte will be played. Patients will be told that their goal is to accrue as many successful trials as possible, and that the height of the bar can be influenced by imagining movements using the stroke affected limb (specifically, the stroke affected finger muscles).

This block of neurofeedback takes approximately 6 minutes, and is repeated three times during the course of the training session, with rest breaks for the patient between blocks.

At the end of the training session, we will record MEPs from 20 TMS pulses while the patient is at rest, viewing a fixation cross (for pre-post measurement of resting corticospinal excitability).

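### Time since stroke drives both changes in the planned MEP–function correlation, so an unadjusted correlation can be positive without any neurofeedback effect

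*Protocol*

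**What the plan says.** - **Planned association (section 1).** After the hypothesis of larger MEPs than under pseudofeedback, the protocol adds: "We will investigate whether these changes in MEP amplitudes correlate with enhanced or faster than usual functional improvement". It names no MEP interval here and does not say what counts as usual.
- **Shared recovery (section 1).** Spontaneous motor recovery reaches up to 70% of the possible improvement within 12 weeks, and "this time course of recovery coincides with the resolution of corticomotor excitability (MEP amplitudes"), which also reach 70% of normal in that period.
- **Entry (section 2).** "Sub-acute: 2-26 weeks post stroke. Would prefer 2-12 weeks if feasible as there is a critical period in first 12 wks". Patients must also have "Low/No residual movement in lower arm and hand" and be MEP positive.
- **MEP measurement (section 4.5).** RMT is re-measured at each training session. Each block has "20 TMS pulses (at an intensity that is 120% of the RMT"). Resting MEPs are recorded at the end of each training session "for pre-post measurement of resting corticospinal excitability".
- **Follow-up (sections 4.6 and 4.7).** Visits fall 2, 6, 12 and 26 weeks after training. RMT is the measure named for monitoring excitability. The full functional assessment is repeated 6 months after training.
- **Comparator (section 4.5.4).** The pseudofeedback group is the comparator for functional outcome.
- **Allocation (sections 4.1 and 4.2).** At consent, patients are "assigned to Group A or Group B using a computer algorithm". The MEP check comes afterwards: "if the patient has no MEPs in response to TMS, unfortunately they will not be able to participate further in the study", with an optional retry a week later.

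**The concern.** On the protocol's own account, a patient who enters at week 2 has most of the spontaneous recovery still to come, in function and in MEP amplitude alike. A patient who enters after week 12 has little of either. Because every change is counted from training, early entrants tend to show large changes on both measures and late entrants small ones. That alone produces a positive correlation.

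At stake is the mechanistic claim that MEP gain goes with better recovery. Read causally, a positive correlation would be credited to neurofeedback when time since stroke could explain it.

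The order of allocation is a separate, smaller matter. MEP-positive status is an eligibility criterion, yet it is checked after the group has been assigned, so some exclusions will fall after allocation.

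**Working it through.** The protocol gives no alpha, noise level or sample-size derivation, so it has no figure to reproduce.

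**Inputs from the protocol:** n = 20 (10 per group); entry at 2-26 weeks; recovery to about 70% over 12 weeks; training over about 1 week; functional reassessment at 26 weeks.

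**Assumptions:** entry time w uniform on 2-26 weeks; two-sided 5% test; four average curves, f(t) = 0.7(1 − exp(−t/τ)) with τ = 4, 6 or 10 weeks, and f(t) = 0.7·min(t/12, 1); independent noise of equal SD on both changes, as a fraction of normal or maximum; no neurofeedback effect and no link between the two changes except through w.

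**Model:** functional change = f(w+26) − f(w) + noise; MEP change = f(w+d) − f(w) + noise, with d = 1 (training week) or d = 26.

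**Gradient, τ = 4.**
- Entry at week 2: 26-week change 0.7(e^−0.5 − e^−7) = 0.424; training-week change 0.7(e^−0.5 − e^−0.75) = 0.094.
- Entry at week 12: 0.7(e^−3 − e^−9.5) = 0.035 and 0.7(e^−3 − e^−3.25) = 0.008.

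**Induced correlation, τ = 4, noise SD 0.10.** Over uniform entry, the SD of e^(−w/4) is about 0.143. The expected 26-week change then has SD 0.7 × 0.143 = 0.100, and the training-week change 0.7 × (1 − e^−0.25) × 0.143 = 0.022. The two expected changes are proportional, so:
- d = 26: r ≈ 0.100² / (0.100² + 0.10²) = 0.50. The critical r at n = 20 is 0.444.
- d = 1: r ≈ (0.022 × 0.100) / √[(0.022² + 0.10²)(0.100² + 0.10²)] ≈ 0.15.

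**Rejection rates** at nominal 5%, n = 20, 20,000 simulated trials per setting, range over the four curves:

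| Noise SD | d = 1, unadjusted | d = 1, adjusted | d = 26, unadjusted | d = 26, adjusted |
|---|---|---|---|---|
| 0.05 | 18-44% | 5-6% | 96-100% | 5-73% |
| 0.10 | 7-13% | 5-6% | 61-98% | 5-16% |
| 0.15 | 5-8% | 5% | 27-82% | 5-8% |
| 0.20 | 5-6% | 5% | 14-53% | 5-6% |
| 0.30 | 5-6% | 5% | 7-21% | 5% |

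Adjusted means for group and log weeks since stroke at entry.

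**Sensitivity.**
- A logistic curve raises the unadjusted training-week rate to 23% at SD 0.10 and 72% at SD 0.05.
- Adjusting for weeks on a linear scale is weaker: for d = 26 and SD 0.10 it leaves 17% (τ = 4) or 58% (linear to plateau).
- Restricting entry to 2-12 weeks does not remove the problem: for d = 26, SD 0.10 and τ = 4 the rate is 72%, against 62% for 2-26 weeks.
- Eligibility: with patient-specific curves and entry only if under 10-30% recovered, the unadjusted rate is 5-7% for d = 1. For d = 26 it is 9-32% (noise 0.1) or 6-12% (noise 0.2), and 5-8% adjusted.
- If one patient-level curve drives both measures, d = 1 gives 5-9% unadjusted and 5-6.5% adjusted. For d = 26, 5-68% remains after adjustment.

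**Between-group comparison.** Type I error is 4.6-5.5%. Adding log weeks lowers the standard error by 2-27%.

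**Allocation order.** Suppose assignment at consent were perfectly stratified at 12 weeks and 10, 20 or 30% then proved MEP negative (assumed). The continuing arms would differ by two or more early entrants in 13, 27 or 38% of trials.

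**The case against.** **This belongs in the SAP.** The sentence in section 1 fixes no test, interval or covariate, and an SAP that is not shown may supply all three. This stands as far as it goes: the missing interval and the undefined notion of usual are not errors in themselves. What remains is that the protocol describes a common cause of the two quantities it plans to correlate, so the adjustment is needed wherever it is written down.

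**The large rates need a late MEP change.** A reader might take 61-98% as the error rate of this trial. The documents do not support that. The hypothesis and the pre-post resting MEPs point to the training week, and section 4.6 names RMT for follow-up monitoring. The follow-up feedback blocks do yield MEPs, so a late change is possible, but no section proposes one for the correlation. Nor is the training-week test safe in general: it is near nominal only if noise is about 0.15-0.20 of normal or more.

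**There is a comparator.** A reader might infer that improvement has no reference at all. Section 4.5.4 gives the pseudofeedback group for functional outcome, and section 1 describes the usual pattern. Neither removes time since stroke from a patient-level correlation.

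**Rejection is not always an error.** If time drives both changes, the correlation is truly non-zero. That is correct: rejection misleads only when read as a mechanism, which is the stated purpose of the project.

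**The average curves ignore selection and RMT resetting.** Both may lower the rates. Selection was examined above. The effect of re-measured RMT was not modelled, because the protocol gives no figure for it.

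**The allocation order does no demonstrated harm.** The check precedes treatment, and the algorithm may already stratify. Bias would need knowledge of the allocation at the check. What stands is the avoidable exclusion after allocation and the risk to balance and 10:10.

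**Conclusion.** The concern holds for the secondary, mechanistic correlation. By the protocol's own account, time since stroke is a common cause of both changes, and an unadjusted correlation can be positive without a neurofeedback effect. For a training-week MEP change the inflation runs from negligible to serious as measurements become more precise. For a 26-week change it is large unless noise is high. These rates rest on assumed curves, uniform entry and assumed noise, so they show a range and do not estimate this trial's error rate.

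The documents do not support reading this as bias in the randomised comparison of MEP change or function. There, time since stroke affects only precision and chance balance. The allocation order is a lesser, separate point about exclusions after assignment, and an amendment can still change it for patients not yet allocated.

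**What to change.** **Main change.** State the association as a regression of functional change on MEP change over the training week (for example, baseline to the resting MEPs at the end of session 4), adjusted for group and log weeks since stroke at entry. Usual improvement then means that expected at the patient's time since stroke. Add a quadratic log-weeks term as a sensitivity analysis. Report later MEP intervals as descriptive, because log-week adjustment does not reliably repair them. Settle this before data are seen.

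**Between-group model.** Include log weeks since stroke, for precision.

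**Allocation, separately.** Assign groups after MEP-positive status is confirmed, including after any retry. This avoids exclusions after allocation and protects 10:10. It does not cure the correlation.

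**Cost.** One or two of the 18 degrees of freedom (one more in the sensitivity analysis), using a value known at screening. For patients not yet allocated, the new order only moves one step within visits already planned.

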4.1 Informed Consent and Providing Information

The patient should be asked to read through the information sheet prior to coming to the first day of the experiment. However, when they arrive for the first session, provide them again with the information sheets and go through them page by page reading and explaining everything to them, answering any questions. When the patient has understood everything, read through the consent form with them, answering any questions, and if they consent to participate ask them to sign their name. If they are unable to sign the consent form, their next of kin can provide consent by proxy. At this stage they will be assigned an

anonymous code which will be used to identify their data and assigned to Group A or Group B using a computer algorithm.

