4.2 Familiarisation Session

This can be conducted on the same day as the signing of the informed consent forms. The patient should be given the opportunity to experience the feeling of TMS prior to commencing with the experimental sessions. The participant will have a fabric cap placed on their head, with a grid drawn on it, indicating the midpoint (vertex) of the head and locations relative to it. The TMS coil will be positioned on the head over the motor cortex on the healthy hemisphere (5cm lateral and 1cm anterior from the vertex), and a weak magnetic pulse applied. The patient will be asked whether they can feel anything. The intensity of the pulses will then be turned up gradually, asking the participant with each increment if the pulse still feels comfortable. When the stimulation intensity is sufficient to evoke a response (MEP) in the index finger muscle of at least 50uV, 5 such pulses will be applied with intervals between 6-8 seconds, to establish the average MEP amplitude at this scalp location. The coil position will then be moved left and right, forwards, and backwards at 1cm increments relative to the starting position, until the position with the largest and most reliable MEPs is located (the motor 'hotspot'). On the hotspot, the experimenter will next establish the patients *resting motor threshold* (RMT). That is, the lowest stimulation intensity that produces MEPs greater than 50uV on 5/10 trials.

When the hotspot and RMT have been established on the healthy hemisphere, this procedure will be repeated on the stroke affected hemisphere, guided by the knowledge of motor cortex positioning on the healthy hemisphere. The RMT is typically much higher on the stroke affected hemisphere, so a higher intensity of stimulation will be required to evoke responses. The RMT for both hemispheres will be noted for future reference, and the position of the hotspot on both hemispheres will be noted on the fabric cap. This is to assist positioning of the TMS coil for all subsequent sessions and negate the need for extensive mapping of the scalp on each new day of testing.

The patient will then be familiarised with the mental imagery requirements of the protocol. They will then be asked to imagine the *feeling* of performing movements with the stroke affected limb and told that this type of imagery will be required to influence the amplitude of their MEPs during the training sessions.

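### Patients are assigned to a group at consent, before the MEP entry criterion is tested, so some assigned patients will be removed after allocation

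*Protocol*

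**What the plan says.** - **Entry criterion (Section 2).** The listed characteristics include "MEP positive (in response to TMS". The planned size is "20 patients (10 in TMS NF group, 10 in Pseudo-feedback group".
- **Allocation (Section 4.1).** Once the consent form is signed, the patient receives an anonymous code and is "assigned to Group A or Group B using a computer algorithm".
- **MEP test (Section 4.2).** The familiarisation session follows consent, on the same day or later. The coil is moved in 1 cm steps "until the position with the largest and most reliable MEPs is located", with a 50 uV criterion for a response. The search is done on the healthy hemisphere and then repeated on the affected one.
- **Removal (end of Section 4.2).** The protocol says that "if the patient has no MEPs in response to TMS, unfortunately they will not be able to participate further in the study", with an alternative: "or, if willing, try again in a week to see have MEPs recovered".
- **Blinding (Section 4.3).** The only measure stated is that the functional assessor is not the person who performs the TMS.
- **Difference between groups (Section 4.5.4).** Only the on-screen feedback differs; the TMS itself is the same in both groups.

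**The concern.** A criterion that decides who may be in the trial should be settled before the group is assigned. Here an assigned patient can be taken out because of a test result obtained after assignment, and that result is closely tied to what the trial measures. The hypothesis in Section 1 is that "training using TMS-neurofeedback will lead to increases in MEP amplitudes, compared to a control group receiving pseudofeedback", and the same section says that the presence of MEPs "has been shown to predict better subsequent functional recovery".

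The test leaves some room for judgement. For a patient who responds, the search has an end point. For a patient in whom no response has been found, there is no stated limit on how long to search, and there is no cap on weekly retests. If borderline patients were searched for longer, or retested more readily, in one group, the groups would differ in excitability before any training began.

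The protocol also does not say whether the 10 per group counts patients assigned or patients found eligible, nor what becomes of the assignment of a removed patient.

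**Working it through.** **Order of events**

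| Step | Protocol section | Event |
|---|---|---|
| 1 | 4.1 | Consent, code, assignment to A or B |
| 2 | 4.2 | First described MEP test |
| 3 | 4.2, end | No MEPs: leave, or optional retest in a week |
| 4 | 4.3, 4.4 | Baseline assessments, MRI |
| 5 | 4.5 | Training; group first affects what the patient sees |

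No MEP screen before consent is described, and step 3 shows that failures are expected at familiarisation. Nothing in steps 2 to 4 needs the group. The cognitive and functional baseline tests also come after assignment, but no removal is stated there and an earlier cognitive screen is not excluded. The problem is therefore the MEP criterion.

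**Size**

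The protocol gives no alpha, power, effect size or SD, so there is no planned figure to reproduce. It gives no MEP-negative share either, only that most patients have MEPs. Everything below is an assumption used for scale: two-sided t-test, alpha 0.05, and a standardised difference of 1.325, chosen because it gives 80.0% power at 10 per group.

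*1. Imbalance when removal is unrelated to group.* To keep 20 eligible patients, 20/(1 − share) must be assigned, rounded up. Given balanced assignment, the split of the 20 retained is hypergeometric.

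| MEP-negative share | Assigned | Removed | P(10:10) | P(12:8 or worse) |
|---|---|---|---|---|
| 10% | 23 | 3 | 0.41 | 0.09 |
| 20% | 25 | 5 | 0.36 | 0.16 |
| 30% | 29 | 9 | 0.30 | 0.25 |
| 40% | 34 | 14 | 0.27 | 0.30 |

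The exact 10:10 split would usually be lost, but the cost is small. For 12/8, the standard error ratio is √(1/12 + 1/8) / √(2/10) = 1.0206, an increase of 2.1%. Power is 79.6% at 11/9, 78.4% at 12/8 and 76.2% at 13/7.

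*2. Lost patients, if 10:10 counts assigned patients and none is replaced.* With binomial loss from 10 in each group, average power falls from 80% to 74.7%, 68.3% and 60.9% for shares of 10%, 20% and 30%. If places are refilled, this loss disappears.

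*3. Differential removal.* Ten are analysed per group. One group began with 11 or 12 and lost its one or two weakest responders; the other lost none. The standard error of the difference is √(2/10) = 0.447 SD.

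- Mean of the top 10 of 11 standard normals: 0.159 SD, and 0.159/0.447 = 0.36 standard errors.
- Mean of the top 10 of 12: 0.275 SD, and 0.275/0.447 = 0.61 standard errors.

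| Correlation of entry MEP strength with outcome | Shift, 1 or 2 removed | Simulated false-positive rate, 1 or 2 removed |
|---|---|---|
| 1.0 (ceiling) | 0.16 or 0.27 SD | 7.5% or 11.3% |
| 0.5 | 0.08 or 0.14 SD | 5.5% or 6.3% |
| 0 | none | nominal 5% |

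Repeat simulations agree to within about 0.2 percentage points. The shift favours whichever group lost its weak responders.

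**The case against.** The strongest reply is that removal is mostly forced. Training pulses are set at 120% of the resting motor threshold, and that threshold is defined by MEPs above 50 uV on 5 of 10 trials. A patient with no MEPs has no threshold and could not be trained in either group. The test also precedes any feedback, so the intervention cannot influence who is removed. Bias needs borderline patients and an operator who both knows the group and acts on it, and the protocol states neither. The A/B labels may be masked codes.

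The size can be challenged too. A correlation of 1.0 is a ceiling: the hypothesis concerns increases in MEP amplitude, stimulation is scaled to each patient's own threshold, and feedback is relative to the patient's own baseline. At a correlation of 0.3 the false-positive rate is about 5.2% or 5.4%. Adjusting for entry MEP strength (correlation 0.5, two removed) brings it back to 5.0%, and such adjustment may be planned in a SAP that is not shown. The power loss needs a no-replacement reading, whereas Section 2 reads more naturally as 10 eligible patients per group.

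Most of this stands, and it limits the consequence to a conditional and probably small one. It does not change the order of events. If everyone involved in the MEP test and retest decision were blind to group, bias would not arise, but the protocol does not say that they are. Even then, assignments would be lost and the 10:10 split disturbed.

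**Conclusion.** The concern holds and should be fixed. The protocol itself sets the time of allocation before an entry criterion is tested, and then removes assigned patients who fail it. That much is certain from the text and depends on no assumed number.

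The harm is a risk left open, not a bias shown to exist. Imbalance alone is minor. The power loss applies only if 10:10 counts assigned patients and removed ones are not replaced. The bias figures require every removal to fall in one group and to take exactly the weakest responders; at a correlation of 0.5 they are modest. The case for acting is that the risk lies on the trial's own outcome measure, the trial has only 20 patients, and avoiding it costs almost nothing.

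**What to change.** End the last sentence of Section 4.1 at the anonymous code and delete the group assignment there. Insert immediately before Section 4.5:

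> Group A or B is assigned by computer algorithm only after MEP positivity and all other Section 2 criteria are confirmed and the Section 4.3 baseline assessments are complete, immediately before training session 1. The 10:10 target counts patients assigned at this point.

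Patients without MEPs then become screening failures, and those awaiting a retest are still in screening. No assigned patient can be removed for failing this criterion, and a balanced list of 20 gives 10:10 by design.

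The cost is one clause moved and a short insertion. It needs no extra visits, patients or staff, and the number to be consented and screened is unchanged (23 to 34 under the assumed 10% to 40% MEP-negative share).

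Reordering does not by itself conceal the next assignment. If that could be predicted, discretion over retests could still affect who enters. A sentence saying that the person doing the MEP test cannot see upcoming assignments would close that remaining route.

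### Allocation is not described as random and names no balancing factor, although the protocol itself treats time since stroke as strongly prognostic and has only 10 patients per arm

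*Protocol*

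**What the plan says.** The whole allocation method is in Protocol section 4.1: at consent the patient receives a code and is "assigned to Group A or Group B using a computer algorithm". Nothing elsewhere adds randomness, blocking, stratification, minimisation or a patient factor. Section 2 sets the size, "20 patients (10 in TMS NF group, 10 in Pseudo-feedback group", and the entry window: "Sub-acute: 2-26 weeks post stroke. Would prefer 2-12 weeks if feasible as there is a critical period in first 12 wks".

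The Overview explains why that window matters. On function: "Within the first 12 weeks, a degree of spontaneous proportional recovery of motor function typically occurs", put at up to 70% of what the patient could still gain. On corticomotor excitability (MEP amplitude): "which also resolves to 70% of normal levels within the same 12 week period". The stated hypothesis is that "training using TMS-neurofeedback will lead to increases in MEP amplitudes, compared to a control group receiving pseudofeedback".

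The four training sessions should ideally fall within 7 days (section 4.5.1). Follow-up sessions come 2, 6, 12 and 26 weeks later (section 4.6), with the full functional, cognitive and MRI assessments repeated at the last one (section 4.7). MEP status is established at familiarisation (section 4.2), which comes after group assignment in 4.1. A patient without MEPs then cannot continue, or may try again a week later.

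**The concern.** On the protocol's own account, a patient entering at week 3 has most spontaneous recovery still to come and a patient entering at week 20 has most of it behind them. Time since stroke therefore predicts change in either arm, for function and for the hypothesised outcome. It is known before allocation, so balancing on it needs no new data.

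With 10 per arm, one arm can easily receive clearly more early patients. That arm would show more spontaneous gain, and a reader of a 20-patient trial would find this hard to separate from an effect of neurofeedback. How patients are allocated is trial conduct. An analysis plan can adjust for an imbalance, but it cannot supply balance or make an assignment random after the fact.

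**Working it through.** **The plan's own figure.** The 10 per arm comes with no effect size, SD, alpha or power, so it cannot be re-derived.

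**1. Chance split of early patients.** Suppose 10 of the 20 enter by week 12 (assumption) and allocation is random with 10 per arm. Then P(x early in one arm) = C(10,x)·C(10,10−x)/C(20,10), with C(20,10) = 184,756.
- 7:3 or worse: 2 × (14,400 + 2,025 + 100 + 1)/184,756 = 33,052/184,756 = 0.179. Half of this, 0.089, favours either given arm.
- 8:2 or worse: 2 × (2,025 + 100 + 1)/184,756 = 0.023.
- With 8 early patients, 6:2 or worse: 0.170. With 6, 5:1 or worse: 0.141. By symmetry the same holds for 12 and 14.

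The probability of a gap of at least 4 early patients is therefore 0.14 to 0.18 across these mixes.

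**2. Imbalance in weeks.** Assume entry is uniform over 2 to 26 weeks. SD = 24/√12 = 6.93 weeks. The SD of the difference in arm means is 6.93 × √(2/10) = 3.1 weeks, with a 95% range of ±6.1. Stratifying at 12 weeks brings the SD to about 1.7 by simulation.

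**3. Imbalance in spontaneous gain, by horizon.** Assume a 50-point deficit of which 70% is recoverable, so the gain still to come at week t is 0.7 × 50 × exp(−t/τ). With τ = 4.0, 5.2 or 8 weeks, recovery is 95%, 90% or 78% complete by week 12. The simulated SD of the arm difference in all remaining gain is 2.25, 2.66 or 3.14 points unstratified, and about 1.6, 1.8 or 1.8 stratified. The gain over the next h weeks is the remaining gain times 1 − exp(−h/τ), so the unstratified SD scales by that factor:

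| Horizon h | τ = 4.0 | τ = 5.2 | τ = 8 |
|---|---|---|---|
| 1 week | 2.25 × 0.221 = 0.5 | 2.66 × 0.175 = 0.5 | 3.14 × 0.118 = 0.4 |
| 6 weeks | 2.25 × 0.777 = 1.7 | 2.66 × 0.685 = 1.8 | 3.14 × 0.528 = 1.7 |
| 26 weeks | 2.25 × 0.998 = 2.2 | 2.66 × 0.993 = 2.6 | 3.14 × 0.961 = 3.0 |

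The issue is small over the training week and several times larger from 6 weeks on.

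**4. Scale against a treatment effect.** The protocol gives none. For orientation, assume two-sided 0.05 and 80% power. Ten per arm then detects (1.960 + 0.842) × √(2/10) = 1.25 SD, or 1.32 SD with the t distribution. A 7:3 split shifts the arm difference by (0.7 − 0.3) × the early-late gap in outcome:
- Gaps of 0.5, 1, 1.5 and 2 SD (assumptions) give shifts of 0.2, 0.4, 0.6 and 0.8 SD.
- To equal 1.25 SD, the gap would have to be 1.25/0.4 = 3.1 SD at 7:3, or 1.25/0.6 = 2.1 SD at 8:2.
- To equal a moderate 0.5 SD effect at 7:3, a gap of 0.5/0.4 = 1.25 SD is enough.

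**The case against.** **A reader might infer that the algorithm uses nothing about the patient, or is a coin flip.** Section 4.1 says neither. An unspecified algorithm could balance on a factor, and section 2 fixes 10 and 10, which a coin flip would give with probability only 184,756/2^20 = 0.18. What stands is that no factor is named and randomness is not stated.

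**A reader might infer bias, or an imbalance as large as the treatment effect.** Under random allocation, chance imbalance is already reflected in the standard error. No treatment effect or early-late gap is given, and against the effect that 10 per arm can detect, the gap would have to be 2 to 3 SD.

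**Adjustment may do the job alone.** This objection is strong. In the model of step 3, with residual SD 5 points (assumption), the SD of the estimated arm difference is about 2.8, 2.9 and 2.9 with stratification and no adjustment. It is about 2.7, 2.7 and 2.6 with linear adjustment for weeks and no stratification. With residual SD 10 the figures are 4.8, 4.8 and 4.9 against 4.8, 4.8 and 4.7. Adjustment thus recovers about as much precision as stratification. The analysis plan is not available here and may already provide it. Stratification still gives visible balance that does not rest on a fitted model, which matters with 20 patients.

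**A 12-week stratum may do nothing.** Section 2 also says "Would prefer 2-12 weeks if feasible as there is a critical period in first 12 wks". If every patient enters by week 12, the late stratum is empty and the SD of the imbalance stays at about 2.4 to 2.6 points, stratified or not. This stands and argues for allowing finer bands.

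**Balance at consent can be undone.** Patients found to have no MEPs leave after assignment, which breaks blocks and strata. This also stands, and it changes the remedy.

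**Conclusion.** The point holds as a cheap design improvement. Section 4.1 does not establish that allocation is random, and it names no balancing factor, although the protocol marks the first 12 weeks as the period of spontaneous recovery and admits patients up to week 26.

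A 7:3 or worse split of 10 early patients has probability 0.18, which assumes a 10/10 early-late mix and random allocation in equal arms. The figures in points further assume uniform entry and exponential recovery on a 50-point deficit. They show the pattern over time and are not forecasts for a particular scale.

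The consequence is lost precision and a result that is harder to interpret, chiefly at 6 to 26 weeks. The documents do not support a claim of systematic bias, of equal harm to every comparison, or of an imbalance as large as the treatment effect.

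**What to change.** In section 4.1, replace the reference to an algorithm with a statement along these lines: once MEP-positive status has been confirmed at familiarisation, patients are randomly allocated 1:1 by computer, stratified by time since stroke (12 weeks or less, more than 12 weeks), in permuted blocks of randomly varied small size (for example 2 and 4). Minimisation with a random element is an equal alternative. It is preferable if most patients are expected before week 12, because it can use weeks since stroke in finer bands. With 20 patients, one factor is about the limit.

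Include weeks since stroke as a covariate in the between-arm comparisons, unless the analysis plan already does so.

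The cost is a line or two of protocol text, a small change to the allocation program and moving assignment from consent to after the MEP check. No extra patients, visits or tests are needed. The downsides are slight predictability of small blocks, which varied block size or the random element limits, and one degree of freedom for the covariate.
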